The number of people reporting poor mental wellbeing is increasing, with rates exceeding 25% of the population. Rates of psychological distress in young people (aged 15-24 years) increased from 19.7% to 26% between 2019 and 2021, with one in five (21.2%) reporting high or very high levels of distress [1]. Whilst several treatment options are available, the most accessible are pharmacological interventions which take time to be effective, have unwanted side effects, and fail to take into account cultural beliefs and practices [2]. Access to professional help and support for psychological distress is also an issue with young adults reporting the highest rates of unmet need in the population (15.5% for 15–24 years and 11.5% for 25–34 years) [3]. Meditation and mindfulness are reported to be effective in decreasing stress and enhancing mood [4, 5] but time, practice, self-motivation and patience are required to fully realise the benefits. Indeed, some authors suggest that the adhering to the meditation sessions or mindfulness programs may become a source of stress [6]. Given the high rates of distress, and difficulties accessing professional mental health support, there is a need to explore alternate options that are easily accessible and can be made readily available to young people to improve their mental health and wellbeing.

Music and sound have been used for centuries to aid relaxation and improve mood [7]. Many people use music to help them relax and sleep better, which has been confirmed as effective in studies with general population and clinical samples [8-11]. Music has long played a key role in young peoples' lives, and serves a variety of purpose including helping to regulate emotions, expressing ones identity and relating to others [12]. Young people tend to choose music to match the context or situation with high- arousal music chosen for exercise and low arousal music for relaxation [13]. Listening to music prior to classes at school, led to improvements in mood, motivation, concentration and learning [14]. These effects were explained by the music creating positive emotions, increasing attention, and providing routine and rest between classes [14]. Music based therapies are also reported to reduce depression and anxiety in adolescents [15], and in university students listening to music had significant effects on both subjective stress and salivary cortisol levels, with the most profound effects being seen when using relaxation music [16].

Sounds with a repetitive beat are traditionally used by Shamans to enter trance like states, and Tibetan monks also use sound when practicing meditation. Sound healing has been used by cultures across the world, for example, the Didgeridoo has been used by aboriginal tribes in Australia for over 40, 000 years [7]. Relaxation music played on “singing bowls” (Himalayan or Tibetan metal bowls or quartz crystal bowls) is readily available and is reported to have rapid, remarkable benefits on stress, mood and sleep. One clinical study in adults, using a pretest-post-test design, reported that an hour-long session of listening to metal and quartz crystal singing bowls resulted in an immediate mean 71% reduction in negative mood scores on the Profile of Mood States [16]. Another study used a randomised sequential crossover design to test the effect of adding either a 12 minute session of silence or listening to Himalayan singing bowls, prior to a 20 minute session of directed relaxation; the singing bowl intervention produced greater beneficial effects on physiological stress measures and mood [17]. In addition, another study reports that a single session of listening to Tibetan singing bowls led to greater physiological and psychological relaxation response (as shown by EEG and heart rate variability) compared with progressive muscle relaxation [18]. There is also preliminary evidence of the efficacy of Tibetan singing bowls in improving mood in young people; using a pre -test post-test design, one 25 minutes session of relaxation music played on quartz crystal singing bowls to a small group (n=11) of NZ adolescent males significantly reduced depression scores (on the Profile of Mood States) immediately after the session, as well as lowering tension scores [19].

Taken together these findings suggest that relaxation music played on singing bowls may be beneficial in improving mood, decreasing stress, and improving sleep. Extending the previous work by co-PI [name] [19], this study seeks to compare the effects of listening to quartz crystal singing bowl music with guided relaxation on mood, stress and sleep in a larger sample of young adults. Participants will be randomly assigned to either the singing bowl (SB) or guided progressive muscle relaxation (PMR) condition. Participants will be asked to listen to singing bowl music or complete the PMR exercises for 10 minutes three time a week for four weeks (delivered online via the Qualtrics platform) and will then be given free access to the music or guided meditation for another four weeks whilst their use is monitored. Ratings of mood, stress and sleep will be completed at baseline, 4 weeks and 8 weeks. For one session per week, participants will be asked to complete visual analogue rating scales of their mood/stress immediately before and after the session to determine the acute effects of the intervention.

3. Study Design and Method

a) Hypothesis

Listening to singing bowl music will result in equivalent improvements in mood, stress and sleep compared with guided relaxation immediately after the session, and at 4- and 8-weeks post-intervention.

b) Design

Randomised controlled trial.

c) Intervention

Singing bowl music (SB)

The singing bowl relaxation music ('Tranquility' available on Spotify) was played by [name] and professionally recorded. The sound is produced by tapping the bowls and rubbing them with a rubber mallet. Each session took approximately 10 minutes.

Guided relaxation (PMR)

A guided progressive muscle relaxation audio (recorded by the NZ Cancer Society <https://www.youtube.com/watch?v=Zydrp3rfJdY>) and similar to the PMR script from the Anxiety and Phobia Workbook by Edmund Bourne [20]) was used. The session took approximately 12 minutes. Participants were instructed to start by sitting or lying comfortably, taking some deep breaths and then tense and relax muscles in a sequential manner from the head to the feet (see Appendix 6 for an example of the PMR script).

d) Outcome measures

Profile of Mood States Abbreviated [21]. Participants are presented with a list of 40 words that describe feelings people have. They are asked to circle the number that best describes how they feel right now from 0 (not at all), 1 (a little), 2 (moderately), 3 (quite a lot) to 4 (extremely). Alogue scales - . A Total Mood Disturbance score (TMD) is also calculated by summing the totals for the negative subscales (Tension, Depression, Anger, Fatigue, Confusion), and subtracting the totals for the positive scales (Vigour, Esteem-related Affect [Note that 2 item are reverse scored for the ERA subscale]). See Appendix 3. The primary outcome measure is the TMD, but we will conduct secondary analyses to examine the effects of the interventions on the subscale scores.

Modified Auckland Sleep Questionnaire [22]. The Auckland Sleep questionnaire was developed to diagnose common sleep disorders in primary care. We will use the items about current sleep and asked participants to rate them in reference to the previous week (rather than the previous month as in the original questionnaire). The overall sleep quality rating will be used in the analysis (Appendix 4).

Visual Analogue Scales

To assess the acute effects of the intervention, participants will be asked to complete ratings of overall mood, relaxation, and stress before and after one session each week. Participants are asked to rate how they are feeling *right now* using a visual analogue scale (VAS) from 0 (worst I've ever felt not relaxed, not stressed,) to 100 (very stressed, very relaxed, best I've ever felt)[23, 24] see Appendix 5.

e) Objectives

Primary Objective

To determine if the effects of listening to singing bowl music are equivalent to that of progressive guided muscle relaxation on self-report measures of mood in young adults (Total Mood Disturbance of the POMS) at 4- and 8- weeks post intervention.

Secondary Objectives

To compare the effects of the interventions on:

- Profile of Mood States-Abbreviated (POMS) subscale scores
- Overall sleep quality from the Auckland Sleep Questionnaire
- VAS ratings of mood, stress and relaxation

Exploratory analyses will be undertaken to determine i) how frequently the participants use the interventions in weeks 4-8, and ii) the acceptability of the interventions.

4. Study population

Members of the general population aged 16-25 years will be recruited to participate in the study. To be eligible to take part, potential participants need to have good hearing, good understanding of English and have a mobile phone or computer to access the intervention and questionnaires via the Qualtrics application. Participants will be excluded if: they are regular users of relaxation music from quartz crystal singing bowls or progressive muscle relaxation, have an untreated mental health diagnosis, or are receiving treatment from a psychologist or psychiatrist. (See Appendix 1 for the eligibility questionnaire).

Participants will initially be recruited from the first-year psychology participant research pool (IPRP) and will receive up to 10% course credit for participation (as outlined in the flyer and participant information sheet (PIS) appendices 7 and 8. Study flyers will also be posted around the University to recruit more widely (participants can choose to enter a prize draw). In the next stage of the study, we will approach secondary schools to advertise the research to their students (subject to additional ethics approval).

We aim to recruit at least 100 participants, with a minimum of 50 university students.

5. Study Procedures

The study/questionnaires will be delivered via the Qualtrics software. Those interested in participating will contact the researchers via a study email address [contact]. Each participant will be allocated to one of the students who will be responsible for monitoring the participant's completion of the questionnaires and sending reminders to complete the intervention as needed. Participants will be sent an individual link to the information sheet, consent form, and eligibility form (Appendices 1, 8). Those meeting the eligibility criteria will automatically be directed to complete the demographic questionnaire (Appendix 2), and the mood (POMS) and sleep measures (modified Auckland Sleep questionnaire) Appendix 3 & 4, (T1).

Participants will then be randomised to either the singing bowl (SB) (Tranquility by [name]) or the guided relaxation group (PMR; example script is in Appendix 6) and given access to the relevant audio on the qualtrics platform (to allow us to monitor when and for how long participants engaged with the intervention). Participants will be asked to listen to the relevant intervention 3 times a week for four weeks (each session is approximately 10 minutes). Before and after one session each week, participants will be asked to complete the visual analogue ratings scales to assess the acute effects of the intervention on their mood, stress and relaxation (Appendix 5). Participants will be sent reminders 3 x per week to complete the intervention.

Participants will be asked to complete the mood and sleep measures again after 4- (T2) and 8-weeks (T3)

The students will actively monitor participant's engagement in the study and send email reminders to complete the intervention sessions (Qualtrics is set up to automatically send email notifications to the study email address when participants complete each session so we can keep track of where they are up to) and the questionnaires at 4 and 8 weeks after the start of the study. After the first four weeks, participants will have free access to either the SB or PMR audio to use as much as they like, and we will monitor the frequency of use via the qualtrics app for the next four weeks. We will send out the link to the intervention weekly in weeks 4-8.

After completion of the 8 week questionnaire (T3) participants will be provided unlimited (and unmonitored) access to both audio tracks and will be asked to provide any feedback on the study.

6. Statistical Analysis

Primary outcomes

Difference scores between baseline (T1) and T2 (4 weeks), and T3 (8 weeks) for the POMS TMD will be calculated.

Secondary outcomes

- a) Difference scores between baseline (T1) and T2 (4 weeks), and T3 (8 weeks) for the POMS subscale scores and Auckland Sleep questionnaire will be calculated.
- b) The number of intervention sessions completed between T1 and T2, and T2 and T3.
- c) Feedback on the acceptability and effectiveness of each intervention.

Sample size

A previous study examining the effects of an in person Tibetan singing bowl (n=62) session showed mean reductions of 0.49 to 1.23 (SD 0.19-1.05) in five POMS subscale scores [16]. A study with a much smaller group of teenage males (n= 11) showed significant reductions in POMS depression scores post-intervention [19]. In person PMR or Autogenic relaxation sessions in young soccer players (n=8) produced significant reductions in four of the six POMS-A subscales (mean difference 2.13 to 4.25; SD 2.38 to 4.47) [25]. As the current study is online rather than in-person, and the sessions are shorter, the effects may be somewhat smaller. Given this we are aiming to recruit a minimum of 100 participants (50 per group). This will provide > 90% power (2-sided $\alpha=0.05$) to detect a medium size effect of the intervention on the POMS subscales.

Analysis Plan

Univariate repeated measures ANOVA will be used to examine the effects of the intervention on the overall TMD score from the POMS, VAS scores and sleep scores. Repeated measures MANOVA will be used to examine changes in the POMS subscale scores.

Participants will be excluded from the analyses if they have not completed at least one intervention session per week for the first four weeks. The number of sessions completed during the first four weeks may be included as a covariate in the analyses.

7. Safety Concerns

Participants will be encouraged to contact us if they have any concerns. We will discuss the issue with the clinical advisor (with the participants consent) and encourage the participants seek support from their GP in the first instance. We will also have a list of support organisations available for participants.

8. Publication

All listed investigators will be co-authors on any presentation or manuscript published from this study. The principal investigators will be the first authors on the study manuscript.

9. References

1. Health Mo. Annual Data Explorer 2022/23: New Zealand Health Survey [Data File]. 2023.

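### Stress is promised and hypothesised at baseline, 4 and 8 weeks, but no stress measure is scheduled at T1, T2 or T3

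*Combined protocol and SAP*

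**What the plan says.** Two places in the combined protocol and SAP put stress at the assessment visits. The last background paragraph, just before Section 3, says "Ratings of mood, stress and sleep will be completed at baseline, 4 weeks and 8 weeks". Section 3a names stress beside mood and sleep and expects equivalent improvement in all three "immediately after the session, and at 4- and 8-weeks post-intervention".

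The sections that put the plan into practice read differently:

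- **Section 5, T1.** After the demographic questions, eligible participants complete "the mood (POMS) and sleep measures (modified Auckland Sleep questionnaire"). At T2 and T3 the mood and sleep measures are repeated, and nothing else is listed.
- **Section 3d, VAS.** Participants are to "complete ratings of overall mood, relaxation, and stress before and after one session each week". The background paragraph gives the purpose: the scales are completed "immediately before and after the session to determine the acute effects of the intervention". Section 5 sets the same weekly schedule next to the four-week scheduled phase and states no end date.
- **Section 3e.** A secondary objective covers "VAS ratings of mood, stress and relaxation", with no time points.
- **Section 6.** T1-to-T2 and T1-to-T3 differences are listed for TMD, the POMS subscales and sleep. The analysis plan assigns repeated measures ANOVA to the VAS scores without saying which ratings enter it.

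**The concern.** Stress is one of three domains in the only hypothesis the trial states, and the overview says it will be rated at all three assessments. If the team builds the questionnaires from Section 5, no rating labelled as stress will exist at baseline, 4 weeks or 8 weeks, and a T3 rating that was never taken cannot be recovered. The authors would then have to drop the 4- and 8-week stress claim or choose a substitute after seeing the data. The obvious substitute, POMS Tension, is already part of the primary score.

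**Working it through.** No figure in the plan bears on this point. The power statement in Section 6 concerns the POMS subscales and is not needed here. The check compares what is promised with what is scheduled.

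**Step 1. Coverage of the three visits** (promise from the background and Section 3a; schedule from Section 5 and Appendices 3 and 4)

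| Domain | T1 | T2 | T3 | Visits covered |
|---|---|---|---|---|
| Mood (POMS) | yes | yes | yes | 3 of 3 |
| Sleep (modified Auckland) | yes | yes | yes | 3 of 3 |
| Stress (designated measure) | no | no | no | 0 of 3 |

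In the T1–T3 questionnaires, stress is mentioned only in Appendix 4, item f, which asks about medication use. None of the 40 words in Appendix 3 is stressed.

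**Step 2. How many VAS stress ratings the plan yields.** In the scheduled phase: 1 session a week × 4 weeks × 2 ratings = 8 at most. If the VAS stops there (an assumption, since no end date is given), the last rating is at about week 4 and T3 is at week 8, a gap of about 4 weeks. If it continued to week 8: 1 × 8 × 2 = 16 at most, of which 16 − 8 = 8 fall in the phase of optional use.

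**Step 3. Can pre-session VAS ratings stand in for T1 and T2?** Only roughly. Appendix 1 lets the first session follow the T1 questionnaires directly, so an early rating could lie close to baseline. But Section 5 introduces access to the audio only at the step that begins "Participants will then be randomised to either the singing bowl (SB"), so every session-linked rating comes after allocation. The plan also does not say which of the week's sessions carries the VAS. Section 6 keeps participants with at least 1 session a week; assume no more than the scheduled 3. The number of sessions before the pre-session rating is then:

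- week 1: 0 to 2
- week 4: from 3 × 1 + 0 = 3 to 3 × 3 + 2 = 11

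**Step 4. Can they stand in for T3?** No. For weeks 4–8, Section 5 describes weekly links and monitoring of use. If the VAS did continue, ratings would come only from participants who chose to keep listening, a group selected after randomisation.

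**Step 5. Does POMS Tension fill the gap?** It is collected and prespecified as a subscale at all three visits, and its content is close to stress. No section names it as the stress measure, and the background lists stress separately from mood. Section 3d forms the TMD by "summing the totals for the negative subscales (Tension, Depression, Anger, Fatigue, Confusion") and subtracting two positive scales, so Tension is 1 of 5 + 2 = 7 components of the primary outcome.

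**The case against.** The strongest reply is that this is a loose overview sentence and not a design gap. The objectives in Section 3e never promise stress at 4 or 8 weeks, the VAS is consistently described as an acute measure, and the recruitment text at the end of the document names only mood and sleep. Sections 3d, 3e and 5 agree with one another; the background sentence and the broad hypothesis are the outliers. Tension is already measured, differenced and assigned to a MANOVA, so one labelling sentence might suffice. It is also only one of seven subscales and therefore not redundant with the TMD. Finally, adding a slider would not by itself test equivalence, because the plan gives no margin.

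Part of this stands. The primary outcome is untouched, wording alone could reconcile the sections, and Tension would carry some information of its own. The session counts in Step 3 describe stand-ins that the plan does not propose, and the conclusion does not rest on them. The missing margin is a real but separate problem that affects mood and sleep equally.

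The reply does not remove the conflict. The hypothesis is what the trial sets out to test, and it names stress at 4 and 8 weeks. Tension can serve only if it is named before the data are seen, with its overlap with the TMD stated. Some words in the POMS paragraph of Section 3d were lost in text extraction, but nothing in Section 5, Section 6 or the appendices suggests that they held a stress measure for the visits.

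**Conclusion.** The concern holds. The plan promises stress ratings at three visits and schedules a designated stress measure at none of them. Followed as Section 5 is written, the 8-week stress hypothesis cannot be tested with a stress measure; at baseline and 4 weeks only approximate, post-randomisation stand-ins exist. The nearest prespecified T3 score, Tension, is a component of the TMD and so is not separate evidence from the primary mood result.

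The 0-of-3 count rests on the text alone. The 4-week gap before T3 assumes that the VAS ends with the scheduled phase; if it does not, the week-8 ratings come only from voluntary users. The damage is confined to one secondary domain, and the change should be made because a missing T3 rating cannot be restored later.

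**What to change.** **If T1 collection has not begun:** add the existing Appendix 5 stress slider to the T1, T2 and T3 questionnaires. At T1 it would precede randomisation. List its T1-to-T2 and T1-to-T3 differences in Section 6 as a secondary outcome, under the repeated measures ANOVA already named for VAS scores. Keep the weekly pre- and post-session VAS as a separate acute outcome, and state when it ends.

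**If T1 collection has begun** (the documents do not say), do one of two things:

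- name POMS Tension in advance as the 4- and 8-week stress measure, stating its overlap with the TMD; or
- limit the stress hypothesis to acute VAS effects and remove stress from the background sentence on the three assessments.

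Two wording points in Section 3a can be settled in the same edit. The acute claim should cover only the VAS items, since sleep is rated over the past week. The 4- and 8-week times should be counted as in Section 5, from the start of the study.

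The cost is one slider that is already written, a few seconds at each of 3 visits, and a small amendment; the fallback options need wording changes only. Neither the interventions nor the primary outcome changes.

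### If university and secondary-school recruits are pooled, no stratification or adjustment by source is described, which leaves avoidable chance imbalance and a small loss of precision

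*Combined protocol and SAP*

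**What the plan says.** All references are to the combined protocol and SAP.

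- **Population (Section 4).** "Members of the general population aged 16-25 years will be recruited to participate in the study".
- **Channels (Section 4).** The first is the psychology pool: "Participants will initially be recruited from the first-year psychology participant research pool (IPRP) and will receive up to 10% course credit for participation". The second is the wider campus: "Study flyers will also be posted around the University to recruit more widely (participants can choose to enter a prize draw". The third is schools: "In the next stage of the study, we will approach secondary schools to advertise the research to their students (subject to additional ethics approval".
- **Composition (Section 4).** "We aim to recruit at least 100 participants, with a minimum of 50 university students". There is no ceiling on university students and no floor for any other group.
- **Allocation (Section 5).** "Participants will then be randomised to either the singing bowl (SB" or the relaxation arm. No sequence method, blocking or stratification factor is given. Section 6 implies equal arms: "Given this we are aiming to recruit a minimum of 100 participants (50 per group".
- **Analysis (Section 6).** TMD is analysed by repeated-measures ANOVA. The only covariate mentioned, and only as an option, is the number of sessions completed.
- **Available data (Section 5 and Appendix 2).** The demographic form is completed before randomisation. It separates people still at secondary school from those at, or finished with, university.

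**The concern.** If both stages run, the trial pools two groups that differ in age and in recruitment period. If mood changes differently in the two groups over four or eight weeks, an uneven split of sources between the arms moves the estimated treatment difference by chance. The primary objective is equivalence, so such a shift could push the result either towards or away from that conclusion. The factor needed to prevent this is known at the moment of allocation, but the plan describes no use of it there or in the model.

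A second, smaller matter is the label on the sample. The composition rule sets a minimum for the group approached first and secures no other group, so recruitment could close with university recruits only, under a heading that speaks of the general population.

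**Working it through.** **The plan's own figure.** The plan gives no figure for source imbalance. The nearest is the power statement, "This will provide > 90% power", for a medium effect that is not quantified. At an assumed effect of 0.5 SD, a two-arm comparison with 50 per arm has 70.5% power. Other tests give more than 90%, for example 93.8% for ANCOVA with an assumed baseline correlation of 0.7. The plan names neither the effect size nor the test behind its figure, so it can be neither confirmed nor refuted. The point here does not depend on it.

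**Inputs.** From the plan: N = 100, 50 per arm, at least 50 university students. Assumed, because the documents give no values: the number S of non-university participants, and the gap g between sources in TMD change, in within-source SD units.

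**Step 1: what the quota permits.** At N = 100, S can be anything from 0 to 50. S = 0 meets both numerical conditions.

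**Step 2: chance imbalance.** With fixed arms of 50 and no stratification, the number X of non-university participants in one arm is hypergeometric (100, S, 50). The between-arm difference in share is (2X − S)/50. For S = 50, Var(X) = 50 × 0.5 × 0.5 × 50/99 = 6.31, so SD(X) = 2.51. The SD of the difference is 2 × 2.51/50 = 0.10, or 10 percentage points.

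| S | P(difference ≥ 10 points) | P(difference ≥ 20 points) |
|---|---|---|
| 50 | 32% | 7.1% |
| 30 | 28% | 4.9% |
| 20 | 21% | 2.3% |
| 10 | 9% | 0.1% |

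Simple coin-toss allocation without fixed arm sizes, simulated, gives 5.7%, 3.0%, 1.4% and below 0.1% in the last column.

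**Step 3: effect on the estimate.** The shift equals imbalance × g. A 20-point imbalance gives 0.20 × 0.2 = 0.04 SD to 0.20 × 0.5 = 0.10 SD. A typical (one-SD) imbalance at g = 0.5 gives 0.10 × 0.5 = 0.05 SD. The standard error of the arm difference within source is √(2/50) = 0.20 SD.

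**Step 4: precision.** In a 50:50 mix, source explains 0.25g²/(1 + 0.25g²) of the variance:

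- g = 0.2: 0.01/1.01 = 1.0%
- g = 0.5: 0.0625/1.0625 = 5.9%

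Leaving source out multiplies the standard error by √1.01 = 1.005 to √1.0625 = 1.031. At an assumed treatment difference of 0.5 SD, power falls from 70.5% to 70.1% (g = 0.2) or 67.9% (g = 0.5), a loss of 0.4 to 2.6 points.

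**The case against.** The strongest reply is that randomisation without strata is valid. Chance imbalance in source is part of ordinary sampling error and is already in the standard error. **This stands.** A reader might infer that the pooled comparison is confounded or biased by source, and the documents do not support that.

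The size also depends on favourable assumptions. The 50:50 mix is the most extreme the quota allows at N = 100, and the risk fades quickly with fewer school recruits. Section 6 works with change from baseline, so stable differences in level between sources cancel. Only a difference in change matters, and nothing in the documents shows that there is one. This stands too, and is why the gain is called small.

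The protocol gives no randomisation method at all. A reader might infer that allocation will definitely be unstratified, but the text supports only that no stratification by source is described. Because schools come later, blocking in time order would balance source to a large extent without a stratum. That answers the concern only if such blocking is used, and none is described.

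On the population, a reader might infer that the protocol promises a representative sample, or that the plan is carried out in full with psychology undergraduates alone. Neither follows. General population can be read as non-clinical, since people under psychologist or psychiatrist care are excluded. The objectives speak only of young adults, and every channel is disclosed. Section 4 also says that flyers will go up and schools will be approached, so a single-pool sample would meet the quota but not the whole recruitment plan. What remains is that the school stage is conditional and no number protects it.

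**Conclusion.** The point holds as a modest, nearly free improvement, conditional on the school stage going ahead. The plan pools sources without describing any use of a baseline factor that it already collects. The comparison stays unbiased.

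The cost is a 7% chance of a 20-point imbalance at an assumed 50:50 mix (2.3% with 20 non-university participants, 0.1% with 10), and about 1 to 6% of outcome variance left unexplained if TMD change differs by an assumed 0.2 to 0.5 SD. If only university recruits enrol, the school-versus-university imbalance does not arise.

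The population wording is a secondary matter of generalisability. It concerns the label in Section 4, not the validity of the comparison. Even with schools included, every named channel runs through an educational institution.

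**What to change.** 1. **Section 5.** If the school stage proceeds, randomise within education status (secondary school versus university/other, from Appendix 2), with a separate balanced Qualtrics randomiser for each group. Set this up before the first school participant is allocated, because it cannot be added afterwards.
2. **Section 6.** Include that factor and its interaction with time in the primary TMD repeated-measures model. The interaction is needed because a main effect alone adjusts for differences in level, not in change.
3. **Section 4 and conclusions.** State that, if schools are not recruited, the sample is young adults recruited through a university. The label university students would be too narrow, since campus flyers may reach non-students.

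**Cost.** One survey branch, one model factor, one or two degrees of freedom and one sentence. No extra participants are needed. Appendix 2 records education, not recruitment channel, so this factor will not separate course-credit from prize-draw participants.
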